3.4.2 Secondary Efficacy Endpoints

The key secondary endpoint is the number of clinically significant infections or episodes of end-organ disease per patient due to AdV, BKV, CMV, EBV, HHV-6, or JCV through Week 26. The definition of clinically significant infections or episodes is the same as for the primary endpoint. The summary statistics will be provided by each individual virus at Week 14 and 26, respectively.

Similar analysis will be performed for the clinically significant infections or episodes of end-organ disease per patient due to AdV, BKV, CMV, EBV, HHV-6 or JCV, from each individual virus through Week 14 and Week 26 (i.e., 6 endpoints each at Week 14 and Week 26).

The mean viral load for each AdV, BKV, CMV, EBV, HHV-6, and JCV virus, obtained as AUC/number of days at Week 14 and Week 26, will be summarized by descriptive statistics in the original and log10 scales. For each virus, the viral load and change from baseline over time will also be summarized in the original and log10 scales.

By-patient listings will be provided for the clinically significant infections or episodes of end-organ disease per patient due to AdV, BKV, CMV, EBV, HHV-6, or JCV.

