6.8. Concomitant Therapy

Clinically available (ie, not investigational) antiviral agents prescribed for other infections, such as foscarnet and ganciclovir to treat CMV, are allowed. Data on their use will be collected along with other concomitant medications.

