6.8.1. Excluded Medications and/or Procedures

All patients may receive available supportive therapy with approved treatments. Investigators should try to maintain stable treatment to the extent possible.

Receipt of other investigational antiviral treatments (eg, brincidofovir or anti-BK virus monoclonal antibodies) within 28 days prior to randomization and throughout the duration of the study is prohibited.

Treatment with supportive regimen therapies, other intravesicular agents for the control of bleeding (including, but not limited to, aminocaproic acid), antispasmodics, treatment for pain control (including opioids), and blood product transfusion support are permitted. Analgesic use will be collected on a daily basis. Clinically available (ie, not investigational) antiviral agents prescribed for other infections are allowed. Use of cidofovir or brincidofovir (eg, for the treatment of AdV) must be discussed with the Medical Monitor prior to initiation. All instances of the use of any antiviral agents during the study will be recorded in the eCRF (including the drug name, dose, and

duration of treatment).

T cell ablative therapies, such as antithymocyte globulin, alemtuzumab (Campath-1H), or other immunosuppressive T cell-targeted monoclonal antibodies, are prohibited during the course of the study. Daily doses of corticosteroids exceeding 0.5 mg/kg prednisone (or equivalent) are prohibited during the course of the study. Should patients require medically a higher dose of steroids, no further study drug will be administered until the steroids are tapered to a dose equivalent of 0.5 mg/kg prednisone (or equivalent) or less.

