9.4.3. Secondary Efficacy Endpoints

The secondary efficacy analysis will be performed on patients in Cohort OL, [REDACTED]

The secondary efficacy endpoints are:

- Time to onset of AdV, BKV, CMV, EBV, HHV-6, and/or JCV viremia at Week 14
- AUC for cumulative viral load for AdV, BKV, CMV, EBV, HHV-6, and JCV over 14 weeks
- Proportion of patients with clinically significant AdV, BKV, CMV, EBV, HHV-6, and/or JCV disease (excludes asymptomatic viremia) through Week 14
- Proportion of patients with clearance of AdV, BKV, CMV, EBV, HHV-6, and/or JCV viremia by Week 8 in HCT patients with detectable viremia prior to the start of treatment
- Proportion of patients with clinically significant AdV, BKV, CMV, EBV, HHV-6, and/or JCV disease and/or end-organ disease as determined by an independent, blinded CAC through Week 26 (the end of the 12-week safety follow-up period)
- Total number of hospital days related to AdV, BKV, CMV, EBV, HHV-6, and/or JCV infection or disease through Week 26
- Proportion of patients with AdV, BKV, CMV, EBV, HHV-6, and/or JCV disease-related mortality through Week 26 as determined by an independent, blinded CAC
- Quality of life assessments, FACT-BMT, EQ-5D-5L, EQ-5D-Y, and EQ-5D-Y Proxy Version 1, through Week 26
- Incidence of overall non-relapse related mortality AdV, BKV, CMV, EBV, HHV 6, and/or JCV disease related mortality as determined by an independent, blinded CAC
- Severity and incidence of acute GVHD
- Severity and incidence of chronic GVHD
- Severity and incidence of CRS
- Severity and incidence of clinically significant cytopenias
- Severity and incidence of renal dysfunction
- Effect on measures of engraftment

Summary tables will be presented by cohort, stratum (Stratum1: Letermovir pretreatment and Stratum 2: No Letermovir pretreatment, and Overall) and [REDACTED]

[REDACTED] For Cohort OL, results will be presented by stratum and overall, as all patients in Cohort OL receive only ALVR105. Combined summary for patients in Cohort OL [REDACTED] will also be provided.

Time to onset of each type of infection (AdV, BKV, CMV, EBV, HHV-6, JCV viremia) and overall will be summarized using Kaplan-Meier method for Cohort OL

Number of patients with onset of AdV, BKV, CMV, EBV, HHV-6, and/or JCV viremia and number of patients censored, and reason of censoring will be presented along with estimate for the median time (days) and its 95% CI.

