9.4.4. Exploratory Endpoints

The exploratory endpoints are as follows

- Detection of anti-AdV, BKV, CMV, EBV, HHV-6 and/or JCV-specific T cells through Week 26
- Hospitalization readmission rate related to AdV, BKV, CMV, EBV, HHV-6 and/or JCV viremia/disease through Week 26
- Total days in the ICU
- Proportion of patients requiring mechanical ventilation related to AdV, BKV, CMV, EBV, HHV-6 and/or JCV infection or disease through Week 26
- Duration of anti-viral therapy (foscarnet, ganciclovir, cidofovir or other) due to viremia and/or disease through Week 26

The exploratory efficacy analysis will be performed on patients in Cohort OL,

For Cohort OL, results will be presented by stratum and overall, as all patients in Cohort OL receive only ALVR105. Combined summary for patients in Cohort OL will also be provided.

Continuous variable will be summarized by descriptive statistics. Categorical variables will be summarized by frequency count and the percentages by visit and overall.

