2.1.3 Exploratory Objectives

Exploratory objectives are as below:

- To determine the incidence and number of re-hospitalizations (following hospital discharge after HCT occurring after randomization) for AdV, BKV, CMV, EBV, HHV-6, or JCV infection or disease through Week 26
- To assess patient-reported quality of life (QoL) through Week 26

- To assess the efficacy of ALVR105 in the proportion of patients with undetectable AdV, BKV, CMV, EBV, HHV-6, or JCV viremia (defined as below the lower limit of quantification [LLOQ]) at Week 14
- To determine hospital length of stay (following initial hospital discharge) for AdV, BKV, CMV, EBV, HHV-6, or JCV infection or disease through Week 26
- To characterize virus specific T cells (VSTs) in patients who were administered ALVR105

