3 STATISTICAL METHODOLOGY

3.1 General Considerations

3.1.1 *Study Day*

Study day will be calculated from the date of first dose of study drug, as actual visit date – first dose date + 1. The day of the first dose of study drug will be Day 1, and the day immediately before and after Day 1 will be Day -1 and Day 2.

3.1.2 *Analysis Visits*

Subject visits might not occur on protocol-specified days. Therefore, for the purpose of analysis, all scheduled, unscheduled, and early termination visits will be assigned to analysis visits according to the analysis windows ([Appendix 1](#)) based on study days. If there is more than 1 assessment in an analysis window, the assessment closest to the target day will be used in the analysis. If there are 2 assessments in a window equidistant from the target day, the later assessment will be used in the analysis.

3.1.3 *Definition of Baseline*

Baseline is defined as the last non-missing measurement prior to the first dose of study treatment. This can be on Day 1 as long as the measurement is taken prior to the first dose.

3.1.4 *Summary Statistics*

Summary statistics will be presented. Unless otherwise stated, continuous variables will be summarized using the number of non-missing observations, arithmetic mean, standard deviation, median, minimum, and maximum values as descriptive statistics. Categorical variables will be summarized using the frequency count and the percentage of patients in each category as descriptive statistics.

3.1.5 *Handling of Dropouts and Missing Data*

In general, data will be analyzed and presented as observed and will not be imputed for the analysis of efficacy and safety, unless otherwise specified.

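### Mean viral load and Week 14 detectability in the open-label cohort include values taken after a treatment antiviral was started, so these descriptive results reflect ALVR105 plus any rescue antiviral

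*SAP*

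**What the plan says.** **Antivirals during the study.** Protocol 6.8 says that clinically available agents "such as foscarnet and ganciclovir to treat CMV, are allowed". Protocol 4.2 leaves treatment of breakthrough disease to the investigator under standard of care. For cidofovir the position is conditional: planned use is an entry exclusion (Protocol 5.2, criterion 11), while Protocol 6.8.1 says "Use of cidofovir or brincidofovir (eg, for the treatment of AdV) must be discussed with the Medical Monitor prior to initiation". Protocol 4.1 keeps patients with a clinically significant infection on study infusions, and the schedule footnotes (SAP Table 6, note n) keep them on all visits through Week 26.

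**Analysis.** SAP 2.1.2 words the AUC objective as efficacy of ALVR105, and SAP 2.1.3 does the same for detectability: "To assess the efficacy of ALVR105 in the proportion of patients with undetectable AdV, BKV, CMV, EBV, HHV-6, or JCV viremia". The mean viral load of each virus, "obtained as AUC/number of days at Week 14 and Week 26, will be summarized by descriptive statistics in the original and log10 scales" (SAP 3.4.2). SAP 3.4.3 gives the number and percentage with detectable viremia at Week 14, by visit and at any visit. Under SAP 3.1.5, in general, "data will be analyzed and presented as observed".

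**Antiviral data.** Protocol 6.8.1: "All instances of the use of any antiviral agents during the study will be recorded in the eCRF". Protocol 6.8.3 adds indication and dates. Protocol 9.4.4 lists as an exploratory endpoint "Duration of anti-viral therapy (foscarnet, ganciclovir, cidofovir or other) due to viremia and/or disease through Week 26". SAP 2.3.3 does not list it. SAP 3.3.5 counts medications by class and preferred term and provides a by-patient listing.

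**The concern.** Patients in whom prevention fails are the ones who receive a treatment antiviral, and that treatment can lower their later viral loads. Those later values enter the AUC and the Week 14 detectability count like any others. In a randomized comparison the control arm would show what background treatment achieves. In this single-arm cohort nothing does, and any distortion favours the product.

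At stake is how two sets of results are read. SAP 3.4.3 itself remarks that most patients are undetectable. A reader of the report will want to know how many reached that state without treatment for the virus in question, and no planned table says so.

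**Working it through.** The plan has no figure of its own to reproduce: the cohort is 25 to 35 patients, with no power calculation and no assumed treatment or clearance rate. The check is first textual, then illustrative.

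**1. Do post-treatment values reach the analysis?** Treatment is allowed, study drug continues and sampling continues, so the values exist. SAP 3.1.5 does not remove them. SAP 3.4.2 and 3.4.3 contain no exclusion, truncation or flag at antiviral start. The only subgroup related to antivirals is letermovir at Baseline. The values therefore enter.

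**2. One patient followed through the SAP.** Suppose CMV viremia is treated in Week 6 and is below the LLOQ at Week 14.
- SAP 3.4.1: one CMV event, because viremia needing treatment counts as a clinically significant infection.
- SAP 3.4.3: not detectable at Week 14, though detectable at any visit.
- SAP 3.4.2: the AUC keeps the rise but adds low values from clearance onward.

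A second patient has clinically significant CMV infection at Baseline and is treated after Day 1. SAP 3.4.1 excludes this patient for CMV, so no failure is recorded there. No such exclusion is stated for the viral-load or detectability summaries.

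**3. Week 14 proportion, for one virus (assumed inputs).** Let r be the share of patients starting a treatment antiviral for that virus, and c the share of those below the LLOQ at Week 14. With complete Week 14 samples, the as-observed undetectable proportion exceeds the proportion undetectable without treatment by r × c. For 30 patients:
- r = 10%, c = 50%: 5 points (1.5 patients)
- r = 20%, c = 50% to 90%: 10 to 18 points (3.0 to 5.4 patients)
- r = 30%, c = 90%: 27 points (8.1 patients)
- r = 50%, c = 90%: 45 points (13.5 patients), an extreme for a single virus

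For example, 24/30 = 80% as observed (exact 95% CI 61% to 92%) becomes 18/30 = 60% (41% to 77%) if 6 of the 24 had been treated. Where r or c is near zero, so is the difference. Because study infusions continue, r × c bounds the contribution of the antiviral from above; some of these patients might have cleared the virus anyway.

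**4. AUC/days for one patient (assumed course).** Viremia starts on Day 30, rises linearly to 10,000 copies/mL on Day 37, and is followed to Day 98 (97 days from Day 1).
- Rise: 7 × 10,000 / 2 = 35,000 copy-days.
- Persisting: 35,000 + 61 × 10,000 = 645,000; divided by 97, 6,649 copies/mL.
- Cleared linearly over 3 weeks: 35,000 + 21 × 10,000 / 2 = 140,000; divided by 97, 1,443.
- Cleared linearly over 2 weeks: 35,000 + 14 × 10,000 / 2 = 105,000; divided by 97, 1,082.

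The ratios are 645/140 = 4.6 and 645/105 = 6.1, or 0.66 and 0.79 on the log10 scale. The comparison assumes that untreated viremia would have stayed at its peak to Day 98, which is the unfavourable extreme.

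**The case against.** The strongest reply is that rescue is already scored as failure where it matters. The primary and key secondary endpoints count viremia needing treatment, and per-virus summaries are given at Weeks 14 and 26. The any-visit detectability summary keeps a cleared breakthrough visible. By-patient listings of medications, viremia and infections would let a reader match treatment to viral load in 25 to 35 patients. Using all values is a legitimate treatment-policy approach. The results are descriptive, and the stated endorsement for Phase 3 rests on a DSMB review after 30 days of treatment.

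All of this stands, and it confines the point to secondary and exploratory summaries. It does not remove it: the SAP never states the treatment-policy choice, the objectives name ALVR105 alone, and listings do not replace a table of treatment timing and duration.

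Four stronger readings are tempting, and the documents do not support them.
- **That the SAP deliberately removed the antiviral-duration endpoint.** The SAP says its analysis follows Amendment 4, and the protocol text at hand cannot be confirmed as that amendment. Other protocol endpoints are also absent, such as time to viremia and ICU days. What can be said is that SAP 2.3.3 explains why the hospitalization and T cell endpoints are not analysed, and nothing explains this one.
- **That clearance results are inflated too.** Clearance of "viremia by Week 8 in HCT patients with detectable viremia prior to the start of treatment" is a protocol endpoint, but the SAP does not analyse it.
- **That one large shift applies to all viruses.** SAP 2.3.3 defines undetectability for each virus, and Protocol 2.3.1 says that five of the six (all but CMV) lack approved or clearly effective treatment.
- **That cidofovir is freely permitted.** Protocol 5.2 and 6.8.1 leave it conditional and should be reconciled.

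**Conclusion.** The point holds within limits. SAP 3.4.2 and 3.4.3 use post-antiviral values without saying so. In a single-arm cohort the mean viral load and Week 14 detectability therefore measure ALVR105 plus any treatment antiviral. This extends to patient-virus pairs excluded from the primary endpoint for infection at Baseline. Any distortion favours the product.

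The size cannot be derived, because the documents give neither treatment nor clearance rates. The figures above show only what assumed rates would imply, and the effect is most plausible for CMV. A reader might infer that the trial's main efficacy result is biased; it is not, since treated viremia is a failure in the primary and key secondary endpoints. The change is worth making before the SAP is finalised, but it concerns the interpretation of supporting results.

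**What to change.** Keep the as-observed summaries and make three additions.

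1. **SAP 3.4.3:** for each virus, add a Week 14 row in which a patient who started a non-prophylactic antiviral indicated for that virus after Day 1 counts as not undetectable. State how a treated patient with no Week 14 sample is counted.
2. **New table, by virus:** number and percentage starting such treatment, time to start, and total duration through Weeks 14 and 26. This covers the antiviral-duration endpoint of Protocol 9.4.4. If it is not to be analysed, give the reason in SAP 2.3.3.
3. **SAP 3.4.2:** state that the AUC includes post-antiviral values and so measures ALVR105 plus any antiviral treatment.

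Splitting the AUC by treatment status, or stopping it at the first antiviral dose, is not needed. The first conditions on a post-baseline event in a small cohort; the second truncates informatively.

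The cost is some SAP wording and a few tables, from drug names, dates and indications that Protocol 6.8.1 and 6.8.3 already require in the eCRF. Recorded indications must be mapped to viruses, which takes judgement for drugs active against several. A less favourable undetectable rate will appear beside the as-observed one. Trial conduct and the primary analysis do not change.

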3.4.3 Exploratory Efficacy Endpoints

The exploratory efficacy endpoints are listed in Section 2.3.3.

The observed and change from baseline in QoL assessments will be summarized through Week 26. Listings will be provided for the QoL assessments.

Since most of the patients are undetectable, the number and percentage of patients with detectable viremia (i.e., \geq LLOQ) will be summarized at Week 14 as well as by visit and at any visit.

By-patient listing will be provided for AdV, BKV, CMV, EBV, HHV-6, and/or JCV viremia and QoL measures.

Subgroup analyses may be conducted for the efficacy endpoints by type (class I or II), the number of HLA matches, and letermovir treatment at Baseline.

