Patients will be tested once a week by the central laboratory during Screening until treatment assignment, using polymerase chain reaction (PCR) assays for each virus. Cohort OL will include patients with and without detectable AdV, BKV, CMV, EBV, HHV-6, and JCV viremia. After Cohort OL, Cohort A will include patients without detectable AdV, BKV, CMV, EBV, HHV-6, and JCV viremia (ie, below the level of quantitation) based on the last viral load assessment available within 7 days prior to randomization, and Cohort B will include patients who are positive with AdV, BKV, CMV, EBV, HHV-6, and/or JCV viremia based on the last viral load available within 7 days prior to randomization, as documented by central laboratory test results. Randomization will occur prior to Day 1. Patients who are positive for >3 viruses will not be eligible to participate.

After HCT, eligible patients in Cohort A and Cohort B will receive either ALVR105 (████████ for patients <40 kg or ██████████ for patients ≥ 40 kg, every 14 days) or placebo every 14 days. Patients in Cohort OL will receive ALVR105 (████████ for patients <40 kg or ██████████ for patients ≥ 40 kg, every 14 days for 14 weeks. Treatment with either ALVR105 or placebo will begin between 15 to 42 (+7) days post-HCT and will continue for 14 weeks. The total duration of patient participation is approximately 28 to 32 weeks, including up to 6 weeks for screening, the 14-week treatment period, and 12 weeks of follow-up.

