3. OBJECTIVES AND ENDPOINTS

Objectives	Endpoints

Primary
 
 1. To compare the efficacy of ALVR105 to placebo in the proportion of patients with clinically significant AdV, BKV, CMV, EBV, HHV-6, and/or JCV infection and/or end-organ disease as determined by an independent, blinded Clinical Adjudication Committee (CAC) through Week 14 	
 1. The proportion of patients with clinically significant AdV, BKV, CMV, EBV, HHV-6, and/or JCV infection (defined as infection and/or end-organ disease as determined by an independent, blinded CAC) through Week 14

Secondary
 
 1. To compare the efficacy of ALVR105 to placebo in time to onset of AdV, BKV, CMV, EBV, HHV-6, and/or JCV viremia over 14 weeks, in patients at high risk, following allogeneic HCT 2. To compare the efficacy of ALVR105 to placebo in area under the curve (AUC) for cumulative viral load for AdV, BKV, CMV, EBV, HHV-6, and JCV over 14 weeks 3. To compare the efficacy of ALVR105 to placebo in incidence of clinically significant AdV, BKV, CMV, EBV, HHV-6, and/or JCV disease (excludes asymptomatic viremia) through Week 14 4. To compare the efficacy of ALVR105 to placebo in the proportion of patients with clearance of AdV, BKV, CMV, EBV, HHV-6, and/or JCV viremia in allogeneic HCT patients with detectable viremia prior to the start of treatment 5. To compare the efficacy of ALVR105 to placebo in the proportion of patients with clinically significant AdV, BKV, CMV, EBV, HHV-6, and/or JCV 	
 1. Time to onset of AdV, BKV, CMV, EBV, HHV-6, and/or JCV viremia over 14 weeks 2. AUC for cumulative viral load for AdV, BKV, CMV, EBV, HHV-6, and JCV over 14 weeks 3. Proportion of patients with clinically significant AdV, BKV, CMV, EBV, HHV-6, and/or JCV disease (excludes asymptomatic viremia) through Week 14 4. Proportion of patients with clearance of AdV, BKV, CMV, EBV, HHV-6, and/or JCV viremia by Week 8 in HCT patients with detectable viremia prior to the start of treatment 5. Proportion of patients with clinically significant AdV, BKV, CMV, EBV, HHV-6, and/or JCV disease and/or end-organ disease as determined by an

Objectives	Endpoints

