4. STUDY DESIGN

4.1. Overall Design

This is a Phase 2, multi-center, randomized, double-blind, placebo-controlled, multiple dosing, trial to investigate ALVR105 administered intravenously, with the first dose between 15 and 42 (+7) days after allogeneic HCT, followed by every 2-week infusions until Week 14, in comparison to matching placebo for the prevention of active replication and clearance of active viremia of AdV, BKV, CMV, EBV, HHV-6, and/or JCV in high-risk patients.

This study is comprised of an optional pre-screening period, a screening period, a treatment period, and a follow-up period. The optional pre-screening period is included to allow for the assessment of viral loads for patients who may potentially be eligible for participation in the study prior to actual screening. The screening period may begin at the time of HCT and may vary in length of up to 6 weeks. The treatment period is 14 weeks, and the follow-up period is approximately 12 weeks. Overall, the total duration patient participation in the study is approximately 28 to 32 weeks (up to 6 weeks for screening, 14 weeks of treatment, and 12 weeks of follow-up). The overall enrollment period is anticipated to be approximately 12 months.

Patients will also receive a telephone call follow-up approximately 52 weeks after their last study visit to assess mortality.

There are 3 cohorts (Cohort Open Label [OL],

The first 25 to 35 patients (Cohort OL) will receive ALVR105 for 30 days of open-label dosing to assess and optimize processes. A review by the Data Safety Monitoring Board (DSMB) will be done when approximately 30 patients have completed 30 days of treatment. At this time an assessment of benefit, risk, and process will be done, and study optimization will be considered.

Open label patients will continue in the open label arm.

Patients will be tested at the first assessment during Screening by the central laboratory for AdV, BKV, CMV, EBV, HHV-6, and JCV viremia using polymerase chain reaction (PCR) assays for each virus. Patients will then be tested weekly during Screening until treatment assignment. In **Cohort OL**, patients may test positive or negative for AdV, BKV, CMV, EBV, HHV-6, and/or JCV viremia.

ohort OL will also include a 50% cap for letermovir prophylaxis; Sponsor can revisit this limit based on on-going assessment of feasibility. With respect to other

prophylaxis treatments see the inclusion criteria ([Section 5.1](#)).

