2.3.3 Exploratory Efficacy Endpoints

The exploratory efficacy endpoints are:

- Proportion of patients with re-hospitalizations (defined as any hospitalization following hospital discharge from HCT or from any subsequent hospitalization before randomization) for AdV, BKV, CMV, EBV, HHV-6, or JCV infection or disease through Week 26
- For patients with re-hospitalizations, number of re-hospitalizations (defined as any hospitalization following hospital discharge from HCT or from any subsequent hospitalization before randomization) for AdV, BKV, CMV, EBV, HHV-6, or JCV infection or disease through Week 26
- Change in QoL, EQ-5D-5L, EQ-5D-Y, and EQ-5D-Y Proxy Version 1, through Week 26
- Undetectable AdV, BKV, CMV, EBV, HHV-6, or JCV viremia (defined as below the LLOQ for each virus) at Week 14
- Number of hospital days related to clinically significant AdV, BKV, CMV, EBV, HHV-6, or JCV infection or disease through Week 26
- Monitoring of anti-AdV, BKV, CMV, EBV, HHV-6, or JCV-specific T cell populations

Since the hospitalization and re-hospitalization data are not collected in the Phase 2 cohort, these endpoints will not be analyzed in this SAP. The anti-viral specific T cell data will not be analyzed in this SAP but reported separately.

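### No planned SAP summary is conditioned on baseline viremia, so the report will contain no clearance proportion for patients who entered viremic

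*SAP*

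**What the plan says.** Protocol 4.1 describes the trial's purpose as "prevention of active replication and clearance of active viremia". The Synopsis states that "Cohort OL will include patients with and without detectable AdV, BKV, CMV, EBV, HHV-6, and JCV viremia". Section 3 of the protocol lists as secondary endpoint 4 the "Proportion of patients with clearance of AdV, BKV, CMV, EBV, HHV-6, and/or JCV viremia by Week 8 in HCT patients with detectable viremia" before treatment starts. Protocol 9.4.3 repeats that endpoint and opens with "The secondary efficacy analysis will be performed on patients in Cohort OL". The text after that point is redacted, but Cohort OL is plainly included.

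The SAP covers only the open-label cohort of 25 to 35 patients. Its objectives (2.1), endpoints (2.3) and efficacy analyses (3.4) contain no clearance endpoint. The nearest item is exploratory: the objective in 2.1.3 is the "proportion of patients with undetectable AdV, BKV, CMV, EBV, HHV-6, or JCV viremia" at Week 14, and the endpoint in 2.3.3 is "Undetectable AdV, BKV, CMV, EBV, HHV-6, or JCV viremia (defined as below the LLOQ for each virus) at Week 14". Section 3.4.3 turns this round: "Since most of the patients are undetectable, the number and percentage of patients with detectable viremia", meaning at or above LLOQ, "will be summarized at Week 14 as well as by visit and at any visit". Sections 3.2.2 and 3.4 set the Safety Population as the denominator for all efficacy analyses.

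Baseline viremia appears in SAP 3.3.3 as a baseline characteristic. It is not among the subgroup factors in 3.4.3, which are HLA type, number of HLA matches and letermovir use.

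**The concern.** Clearance is a question about patients who were viremic at the start. A percentage over all treated patients does not answer it. A patient who cleared and a patient who never had the virus both count as undetectable. A patient who failed to clear and a patient newly viremic both count as detectable. These are opposite outcomes for the product, and the planned tables combine them.

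At stake is a question that the supplied protocol asks and that only the viremic entrants can answer. If the SAP is followed as written, the report will contain no clearance proportion. The all-patient percentage will depend on how many patients were viremic at entry as well as on what happened to them.

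**Working it through.** The documents give no figure to reproduce for this point. The check has two parts: what each planned output can show, and how far the planned percentages pin down a clearance rate.

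**Planned outputs, one by one**

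- *Percentage detectable at Week 14 and by visit (SAP 3.4.3).* Each is a marginal percentage at one time. A Week 8 figure will exist, but it has the same limitation as the Week 14 figure.
- *Percentage detectable at any visit (SAP 3.4.3).* A patient with one detectable visit who later clears still counts as detectable, so this cannot show clearance.
- *Primary and key secondary endpoints (SAP 3.4.1, 3.4.2).* These count new clinically significant infections, and a patient with clinically significant infection by a virus at Baseline is excluded for that virus. They do not address resolution.
- *Viral load change from baseline (SAP 3.4.2).* This is summarised over all treated patients, including those never viremic, and yields no proportion cleared.
- *By-patient viremia listing (SAP 3.4.3).* This holds the raw information but defines no endpoint.

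**Bounds on clearance from the marginal counts**

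For one virus, let N be the patients treated, b the number viremic at Baseline and d the number detectable at a later visit, with everyone sampled at both times. If only b and d are tabulated, then

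number cleared lies between max(0, b − d) and min(b, N − d).

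N comes from SAP 2.2.3 (25 to 35). The values of b and d are assumptions, because neither document gives them.

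| N | b | d | Undetectable, all patients | Cleared among b |
|---|---|---|---|---|
| 30 | 9 | 3 | 27/30 = 90% | 6/9 to 9/9 (67% to 100%) |
| 30 | 9 | 6 | 24/30 = 80% | 3/9 to 9/9 (33% to 100%) |
| 30 | 6 | 6 | 24/30 = 80% | 0/6 to 6/6 (0% to 100%) |

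For N of 25, 30 and 35, b of about 20% to 50% and d of about 10% to 20%, the lower bound runs from 0% to 83% and the upper bound is always 100%.

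**Sensitivity of the all-patient percentage to clearance**

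Let f be the fraction viremic at Baseline, c the fraction of those cleared, and m the fraction of the rest who are detectable later. Then

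undetectable = f × c + (1 − f) × (1 − m).

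With assumed m = 0.05:

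- f = 0.10: c = 0.30 gives 0.030 + 0.855 = 88.5%; c = 0.80 gives 0.080 + 0.855 = 93.5%.
- f = 0.30: c = 0.30 gives 0.090 + 0.665 = 75.5%; c = 0.80 gives 0.240 + 0.665 = 90.5%.

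The gap is f × (0.80 − 0.30), which does not depend on m: 5 points at f = 0.10 (1.5 patients in 30) and 15 points at f = 0.30 (4.5 patients in 30). The level does depend on m. At f = 0.30, 75.5% undetectable also arises with c = 0.80 if (1 − m) = (0.755 − 0.240)/0.70 = 0.736, that is m of about 26%. Poor clearance with little new viremia and good clearance with much new viremia then give the same table entry.

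**Precision of the direct estimate**

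Exact 95% intervals: 6/9 gives 30% to 93%; 9/9 gives 66% to 100%.

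**The case against.** The strongest reply is that the supplied protocol may not govern this SAP. SAP section 1 says the data were collected under Amendment 2 and the analysis follows Amendment 4. The SAP describes a Phase 2/3 study with a count-per-patient primary endpoint and investigator-determined events; the supplied protocol describes a Phase 2 study with a proportion adjudicated by a committee. Section 3 of the protocol also promises only similar endpoints for the open-label part and leaves detail to the SAP. This stands as far as attribution goes: a reader might infer that the SAP itself dropped the endpoint, but it may have gone by amendment, and that cannot be confirmed here. It does not explain the silence. SAP 2.3.3 and 2.3.4 say why hospitalization, T-cell and engraftment items are not analysed; nothing is said about clearance.

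Second, a reader might infer that cleared patients could not be identified at all. That is too strong. With 25 to 35 patients, the viremia listing read with the baseline values would show who cleared. But this would be a post hoc reconstruction by hand, with no rule for antivirals, death or missing samples.

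Third, it is tempting to say that this cohort was enrolled to study clearance. The documents do not support that: Cohort OL was set up to assess and optimise processes, viremia is permitted but not required, and the designated viremic cohort is Cohort B.

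Fourth, it is tempting to read the SAP's remark about most patients being undetectable as saying that most never had the virus. It does not say so; undetectable patients may include cleared ones.

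Finally, Cohort OL has no control arm and antivirals are allowed (protocol 6.8), so a clearance percentage cannot isolate a drug effect. That is right. It limits how the figure may be interpreted and is a reason to present it descriptively, not a reason to omit it.

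**Conclusion.** The point holds in this form: the supplied protocol has a Week 8 clearance endpoint covering Cohort OL, the SAP has none and does not say why, and no planned summary table is conditioned on baseline viremia. The planned percentages therefore do not determine a clearance rate.

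The size depends on counts the documents do not give. Under the assumed counts above, a single all-patient percentage leaves the clearance rate anywhere within an interval that runs from 67%–100% in a favourable case to 0%–100% in an unfavourable one. The bounds assume complete sampling and that baseline viremia is tabulated per virus, which SAP 3.3.3 does not state.

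The verdict does not rest on the reporting being confined to Week 14, since by-visit figures are planned too. It affects no primary result. It is a cheap improvement to a descriptive analysis.

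**What to change.** In SAP 2.3.3 and 3.4.3, add a table, per virus and for any virus. Among patients at or above LLOQ at Baseline, it should give the number and percentage below LLOQ by Week 8 and at Week 14, with:

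- an exact 95% CI;
- a flag for antiviral therapy started before clearance;
- a stated rule for death and for missing samples.

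Split the planned detectable-viremia summary at each visit by baseline status, so that new viremia is shown separately from persistent viremia. Label the results descriptive. If the endpoint was removed on purpose, a sentence saying so and why is the minimum.

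The cost is SAP wording and one table, plus the split. The inputs are in place: SAP 3.1.3 defines Baseline, Appendix 1 has viral load windows for Baseline and Week 8 (Days 54 to 60), and Appendix 2 schedules sampling weekly, or every two weeks for most of the treatment period under age 12 except for AdV. Antiviral use is recorded with concomitant medications. The downside is small per-virus denominators in 25 to 35 patients, which the wide intervals will show openly.
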